The target population for the study are all school children in 5th-7th grade in primary schools in Asker, Moss and Lillestrøm municipalities in the central-eastern part of Norway. Primary schools with more than 200 students and with a school nurse appointed in at least 50% position are eligible for the study. Eligibility for having a support group established is based on the subjective experience of loneliness by the individual child and is defined as a negative emotional state caused by the discrepancy between the desired and actual social relationships, in line with Peplau et al (1).

Clusters and randomization procedure Since decisions about bullying interventions are typically made at the municipal level, we will begin the recruitment process of schools through enrolment of selected municipalities, as illustrated in figure 2. In selected municipalities consenting to participate, we will randomly invite 26 primary schools from the pool of eligible primary schools in these municipalities.

Figure 2. Illustration of the recruitment process of primary schools in xx, xxx and xxx municipalities in Norway

We will continue enrollment until the pre-identified number of schools is reached. The enrolled schools will be sorted by size and then block-randomized in a 1:1 ratio to either the intervention arm (hereafter referred to as intervention schools) or the control arm (hereafter referred to as control schools). A statistician not involved in the study will carry out the randomization procedure. After randomization, the schools will be informed about their assigned cluster and will receive more detailed information accordingly.

Sample size calculation *School level*: Based on the available literature, we anticipate that 6-10% of children in 5th -7th grade will report bullying (Krusell et al., 2019; Wendelborg, 2021). This proportion is expected to be reduced to at least 6 % in intervention schools' post-intervention. With a significance level at 5% and power at 80%, we will need 721 children in each arm. Accounting for additional variation, we would need 793 in each arm. We assume there will be three classes in each school with about 30 children in each class. Thus, we aim to include 26 schools (13 for each arm) to ensure that the study is sufficiently powered.

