Risks. We have conducted a comprehensive assessment of potential risks that could impact the successful achievement of the project's activities, as well as strategies to mitigate them. **Risk 1, Risk of contamination:** The potential for contamination exists due to the dissemination of intervention details among control schools, facilitated by their knowledge of the intervention and prior experiences from the pilot study. This could undermine the integrity of the study's results. However, no schools or staff from the pilot study participated in this study. **Risk 2, Insufficient response rate for inclusion:** To address this risk, our starting point will be the administration in the selected municipalities, as decision to participate in school-interventions is commonly decided upon at this level. If the selected municipalities support participation in the study, we assume that school administrations will be more likely to consent to participate. In the recruitment of schools, we will benefit from *Adults for Children*, as they have substantial experience in engaging schools for analogous initiatives. They will assist in training and supporting school nurses and teachers, ensuring their thorough readiness for implementation and follow-up. This encompasses refining how the project is introduced to foster participant confidence in the project's safety and participation. Additionally, a partnership with the Norwegian Nurses Association will leverage their social media network to generate interest and desire among potential participants. **Risk 3, Delay in completing project activities:** to mitigate this risk, we have established a project team of experienced researchers prioritizing adherence to the project timeline. Furthermore, we plan to submit applications for ethical and GDPR approvals by February 2024, ahead of the projects planned funding period. This proactive approach will head-start project activities. Leveraging insights from the pilot study, we will ensure that REK (Regional Committees for Medical and Health Research Ethics) has timely access to all necessary information for ethical approval considerations. **Risk 4, Time constraints for completing a full PhD:** Acknowledging the study's complexity and the 9-month post-intervention follow-up for study results, the project teams is dedicated to support the PhD-candidate to ensure ample thesis-writing time. We may also involve master students in public health nursing to support the candidate in data-collection and analyses.

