
Follow-up of participants

All study support group participants will receive post-study follow-up consultations with the school nurse or social teacher after the intervention. *Adults for Children*'s experience with research involving children and will carefully address the ethical responsibilities, including how to inform children, in their 3-days training program. Participants from *Adults for Children* and the researchers are available for teachers, school nurses, children, and their parents throughout the study. A safety plan is also prepared for additional support should be necessary after the study concludes. If the intervention yields positive effects, all control schools will be invited to implement the intervention as per protocol soon after the conclusion of the study.

Data protection and statistical analysis

We will seek ethical approval for the study from the Regional Ethical Research Committee (REC) in South-East Norway and ensure compliance with data privacy regulations in line with NSD and EUs privacy regulation GDPR. Data will be collected through and stored in the secured server *Tjenester for Sensitive Data* (TSD), integrated solution for collecting and storing sensitive data, managed by the University of Oslo. This includes recording of interview-data through the use of Nettskjema-diktafon in TSD. This is in line with OsloMet's standards for confidentiality and data protection. A risk assessment with appropriate actions will be conducted prior to study implementation.

Baseline data will be presented descriptively. We will use 1600 children (9 schools in each arm) for comparison between intervention- and control schools on school-level. Generalized mixed models (GLM)

for repeated will be used to explore intervention outcomes on individual level for children who were targeted for support groups. GLM will also be used to analyse possible differences on school level. The results will be reported as the estimated between group changes with 95% confidence intervals.

For the process evaluation, descriptive statistical analysis of quantitative data and content analysis of qualitative data will be carried out.

Quality assurance

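### Randomisation balances on school size only; stratifying by municipality would remove avoidable chance imbalance at almost no cost

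*Protocol*

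**What the plan says.** The Methods section of the protocol takes its target population from "primary schools in Asker, Moss and Lillestrøm municipalities". Under Clusters and randomization procedure, recruitment starts with municipalities, and the reason given is: "Since decisions about bullying interventions are typically made at the municipal level". Risk 2 in the Risks section says much the same about taking part: "decision to participate in school-interventions is commonly decided upon at this level".

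The allocation rule follows in the same section: "The enrolled schools will be sorted by size and then block-randomized in a 1:1 ratio". Size is the only balancing factor named. No block size is given, and nothing in the protocol stratifies or otherwise restricts the allocation by municipality. A statistician from outside the study draws the list after the schools have been enrolled.

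The planned number of schools appears under Sample size calculation: "we aim to include 26 schools (13 for each arm" in brackets. The analysis text under Data protection and statistical analysis gives a different number, "We will use 1600 children (9 schools in each arm". That conflict is a separate matter, but both numbers are carried below.

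**The concern.** The protocol treats the municipality as the level at which action on bullying is usually decided and recruits through it, then ignores it when allocating. With 13 schools per arm from three municipalities, a lopsided split is fairly likely.

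If municipalities differ in bullying level or local practice, a lopsided split adds noise to the school-level comparisons (pRQ1 to pRQ3). A reader of the baseline table may also ask whether a difference between arms is really a difference between municipalities. A covariate added later can adjust for an uneven split but cannot undo it.

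**Working it through.** **The plan's own figure.** For 10% v 6%, two-sided 5% and 80% power, with pooled variance under the null:

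n = [1.960·√(2·0.08·0.92) + 0.842·√(0.10·0.90 + 0.06·0.94)]² / 0.04² = (0.752 + 0.322)² / 0.0016 ≈ 721 per arm.

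This matches the protocol, and 721 × 1.10 = 793. Neither figure is disputed here, and the point does not change the sample size.

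**Inputs for the imbalance.** From the protocol: 3 municipalities, 26 schools, 13 per arm, balance on size only. Assumed, because the protocol is silent: schools per municipality (9/9/8, 10/10/6 or 12/8/6), and a school's size rank unrelated to its municipality.

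**Chance of a lopsided split.** Under that last assumption, blocking on size gives no control over municipality. The split then follows the multivariate hypergeometric distribution:

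P(a, b, c) = C(n₁,a)·C(n₂,b)·C(n₃,c) / C(26,13), with a + b + c = 13 and C(26,13) = 10,400,600.

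The gap in a municipality of n schools, a of them in the intervention arm, is |2a − n|. Summing over allocations where the largest of the three gaps is at least 4, or at least 6:

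| Assumed split | Gap ≥ 4 | Gap ≥ 6 |
|---|---|---|
| 9/9/8 | 3,041,192 / 10,400,600 = 29.2% | 4.7% |
| 10/10/6 | 4,191,320 / 10,400,600 = 40.3% | 8.2% |
| 12/8/6 | 4,117,400 / 10,400,600 = 39.6% | 7.8% |

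Simulation of size-sorted blocks agrees, and block size hardly matters: for 9/9/8, gap ≥ 4 occurs in 29.1%, 28.8% and 29.2% with blocks of 2, 4 and 26. With 9 schools per arm (6/6/6) the figure is 13,620 / 48,620 = 28.0%.

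A gap of 3 or more occurs in 61.5% of allocations for 9/9/8, but that is a poor yardstick. The best split of nine schools is 5:4, so 6:3 is one school away from it.

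**What a lopsided split could do to the bullying contrast.** Ignoring the size blocks, the variance of the raw difference in arm means due to municipality mix is S²·(1/13 + 1/13), where S² is the variance of the municipal rate across the 26 schools (divisor 25).

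- No municipal difference: S² = 0, so the SD is 0.
- Hypothetical rates of 8, 10 and 12% with 9/9/8: mean = 258/26 = 9.92; sum of squares = 67.85; S² = 67.85/25 = 2.714; variance = 2.714 × 2/13 = 0.418; SD = 0.65 points. The other two splits give 0.62 and 0.64.

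The planned difference is 10 − 6 = 4 points. These SDs are for a raw post-intervention comparison. Adjusting for baseline level would reduce them.

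**Does changing the sort order suffice?** Not by itself. Take one list ordered by municipality and then size (9/9/8), in blocks of 4. The second municipality's nine schools fall 3, 4 and 2 into successive blocks. The block of 4 within it is balanced. A 6:3 split needs the 3 to divide 2:1, which they always do one way or the other (the block's fourth school belongs to the first municipality), and the 2 to fall together in the same direction, which has probability 1/6. So 6:3 still occurs in 1/6, about 17%, of allocations. Blocks of 2, or blocks restarted in each municipality with any short last block kept as even as possible, hold the gap to 1 where the number of schools is odd and 0 where it is even.

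**The case against.** The strongest objection is that nothing in the protocol shows municipality to be prognostic. A reader might infer that, on the protocol's own reasoning, bullying rates and usual care differ by municipality. The text does not support that. The remark about municipal decisions explains where recruitment starts, and the Risk 2 remark is about agreeing to take part. The Study design and Study procedure sections tie usual care to national guidelines. This objection stands: the prognostic weight of municipality is an inference.

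A reader might also take the 6% and 13% in the Background as a plausible spread between municipalities. They are national figures that differ by source, year and grade, so no effect size should be built on them.

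Three further points stand.

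- Chance imbalance under randomisation is not bias.
- All students are surveyed at baseline (Table 2) and results are to be reported as between-group changes, so a stable municipal difference would be partly absorbed.
- A municipality term in the model is commonly left to the statistical analysis plan, which is not at hand, so its absence from the protocol is not a fault.

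If school size and municipality are related, the size blocks would already remove some of the imbalance.

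What survives is narrower. The allocation rule is stated in the protocol, it omits the one grouping through which the trial recruits, and including that grouping costs almost nothing.

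**Conclusion.** The point holds as a cheap improvement to the design, not as an error in it. Size-only balancing leaves roughly a 29% to 40% chance that some municipality differs by four or more schools between arms. That range rests on 26 schools, the assumed splits, and size being unrelated to municipality. The consequence is possible loss of precision and credibility, with no bias.

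The effect on the bullying contrast cannot be derived from the protocol. It is nil if municipalities are alike. About 0.6 points of SD before baseline adjustment illustrates one made-up set of rates and is not an estimate.

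**What to change.** Under Clusters and randomization procedure, state that randomisation is stratified by municipality: enrolled schools are sorted by size within each municipality and block-randomised 1:1 separately within each, using blocks of 2 or blocks restarted in each municipality. Include municipality as a factor in the school-level model.

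With 26 schools in three municipalities, either none or two of the municipalities have an odd number. If two do, their leftover schools can be treated as a final pair, which keeps the arms at 13 and 13.

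If schools have already been allocated, report the number of schools per municipality in each arm and adjust for municipality in the school-level model.

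Cost: at most one unpaired school per municipality, slightly looser balance on size, and two degrees of freedom in the model. No extra schools, staff or data are needed, because the list is drawn after enrolment by an independent statistician.

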pRQ4: To what extent do children with a peer support group report a reduction in **bullying** at the end of the intervention compared to their pre-intervention baseline level?

sRQ5: To what extent do children with a peer support group report improved **mental health** at intervention end compared to their pre-intervention baseline level?

sRQ6: To what extent do children with a peer support group report better **quality of life** at intervention end compared to their pre-intervention baseline level?

sRQ7: To what extent do children with a peer support group report increased **general self-efficacy** at intervention end compared to their pre-intervention baseline-level?

sRQ8: To what extent does the effects as measured in R1-R7 persist 6- and 9 months after intervention end compared with pre-intervention baseline level?

sRQ9: To explore the recruitment rate and factors associated with non-participation, on school, provider, and child level.

sRQ10: To describe whether the intervention was delivered according to protocol in terms of quality, quantity, adaptions and variations across schools and time.

[figure not shown]
sRQ11: To describe the intervention acceptability from children's, teachers, school nurses and residents' perspectives.

sRQ12: To investigate barriers and facilitators to intervention delivery and the mechanisms of impact.

Study design

This is a cluster randomized trial of children in 5th to 7th grade in Norwegian primary schools with randomization at school level. The cluster design is well-suited due to the significant risk of contamination between the groups with a regular RCT design. The study flow is presented in figure 1. Intervention schools will implement the SFA-model for reducing bullying, whereas the control schools will offer usual care according to national guidelines. The intervention is at two levels; (i) training of school nurses and school staff and raising awareness about the SFA-model among parents and students; for this part the outcomes will be measured at cluster-level, and (ii) implementing the SFA-model on individual participant level; for this part the outcomes will be measured on individual level in the intervention cluster only. The recruitment process, the intervention and the outcomes measured are described below.

Figure 1 Study flow for the Cluster randomized controlled trial

Methods

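### The school-level sample size uses a formula for individually randomised pupils plus an unexplained flat 10%, with no intraclass correlation, so the stated 80% power is not demonstrated

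*Protocol*

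**What the plan says.** The Study design section fixes the unit of randomisation: "This is a cluster randomized trial of children in 5th to 7th grade in Norwegian primary schools with randomization at school level".

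The school-level paragraph under Sample size calculation gives the expected rates: "we anticipate that 6-10% of children in 5th -7th grade will report bullying" and "This proportion is expected to be reduced to at least 6 % in intervention schools' post-intervention". It continues: "With a significance level at 5% and power at 80%, we will need 721 children in each arm". The only adjustment follows: "Accounting for additional variation, we would need 793 in each arm". Cluster size is then given as "We assume there will be three classes in each school with about 30 children in each class", and the paragraph ends: "Thus, we aim to include 26 schools (13 for each arm) to ensure that the study is sufficiently powered".

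The section Data protection and statistical analysis gives a different number of schools: "We will use 1600 children (9 schools in each arm) for comparison between intervention- and control schools on school-level".

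The Protocol gives no ICC, design effect or between-school coefficient of variation, and no school-level non-response rate.

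**The concern.** In a school-randomised trial, pupils in the same school tend to resemble each other, and the loss of information grows with the number of pupils per school. An inflation that depends on neither the cluster size nor an ICC cannot show that the design has its stated power. The calculation supports the first primary research question, on bullying, which is also the main outcome. If power is well below 80%, a null result could be misread as evidence that the intervention does not work.

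**Working it through.** **Inputs from the Protocol.** Control rate 10% (the upper end of the stated range; 7%, 8% or 9% would need 9540, 2554 or 1209 per arm). Intervention rate 6%. Significance level 5%, taken as two-sided because that reproduces the stated figure. Power 80%. Three classes of about 30, so m = 90 pupils per school. Either 13 or 9 schools per arm.

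**Reproducing 721.** The pooled two-proportion formula, with mean rate 0.08, is

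n = [1.960 × √(2 × 0.08 × 0.92) + 0.842 × √(0.10 × 0.90 + 0.06 × 0.94)]² / 0.04² = 720.9, so 721 per arm.

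This formula contains no clustering term.

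**Reproducing 793.** 721 × 1.10 = 793.1. The allowance is a flat 10%.

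**Clustering that the 10% would cover.** Design effect = 1 + (m − 1) × ICC. Setting this to 793/721 = 1.0999 with m = 90 gives ICC = 0.0999/89 = 0.0011. At a mean rate of 8%, the between-school SD is √(0.0011 × 0.08 × 0.92) = 0.9 percentage points.

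**From 793 to schools.** 793/90 = 8.8, which is 9 schools per arm, not 13. Two arms of 793 make 1586, close to the 1600 children in the analysis section. So the analysis section follows the 793 figure, and the step from 793 to 13 schools is not explained.

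**Clustering that 13 schools per arm would cover.** 13 × 90 = 1170 per arm, and 1170/721 = 1.623. By normal approximation the tolerable ICC is 0.623/89 = 0.0070. With a noncentral t distribution on 2 × 13 − 2 = 24 df, power at ICC 0.007 is 77%, and 80% is reached only up to an ICC of about 0.0056.

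**Power over a range of ICC.** The ICC is an assumption, because the Protocol gives none. Effective n per arm = (schools × 90)/(1 + 89 × ICC). The noncentrality is 0.04/√(0.1464/effective n), where 0.1464 = 0.10 × 0.90 + 0.06 × 0.94.

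| ICC | Design effect | Pupils needed per arm (schools) | Power, 13 per arm: 24 df (normal) | Power, 9 per arm: 16 df (normal) |
|---|---|---|---|---|
| 0 | 1.000 | 721 (9) | 93% (95%) | 79.8% (84%) |
| 0.005 | 1.445 | 1042 (12) | 81% (84%) | 64% (70%) |
| 0.01 | 1.890 | 1363 (16) | 70% (74%) | 53% (58%) |
| 0.02 | 2.780 | 2005 (23) | 54% (57%) | 39% (43%) |

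The third column is 721 × design effect, rounded up, and uses the normal approximation.

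**Detectable rate.** With 13 schools per arm, 24 df, 80% power and a 10% control rate, the detectable intervention rate is about 6.1%, 5.6% and 4.8% at ICC 0.005, 0.01 and 0.02.

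**The case against.** The strongest reply is that the planned trial is larger than 793 per arm. Thirteen schools of 90 give 1170, and by normal approximation that tolerates an ICC of 0.007. At a mean rate of 8% this is a between-school SD of √(0.007 × 0.08 × 0.92) = 2.3 points, or about 3.5% to 12.5% within two SDs. A reader might infer from the 10% step that the whole trial relies on schools barely differing. The document does not support that for 26 schools; the 0.0011 applies only to 793 pupils, or about 9 schools, per arm.

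A reader might also infer that the trial is underpowered. That is not supported either: no ICC is given, and 13 schools per arm reach 81% at 0.005 even with 24 df. Baseline is measured, so adjusting for it might recover some power, although the calculation claims no such gain.

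The Protocol also does not say that the 10% is for clustering. The individual-level calculation adds 10% for dropouts, so this 10% could have had another purpose. In that case the implied ICC has no meaning, but there is then no stated clustering allowance at all.

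These replies narrow the point without removing it. The surplus above 793 is not presented as a clustering allowance. It may also have to absorb refusals and loss to follow-up, for which no school-level rate is given. It is absent from the 9-school comparison in the analysis section.

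**Conclusion.** The point holds as a gap in the demonstration of power. The figures 721 and 793 reproduce; what is wrong is the claim of adequate power for 26 randomised schools when the parameter that governs power in this design is missing. With 24 df, the claim holds for 13 schools per arm only if the ICC is at most about 0.0056. With 9 schools per arm and 16 df, power is just under 80% even at an ICC of zero. Over the assumed ICC range 0.005 to 0.02, power runs from 81% to 54% with 13 schools per arm and from 64% to 39% with 9.

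These figures assume 90 responding pupils in every school, 10% versus 6%, a two-sided 5% test and no gain from baseline adjustment. How serious the gap is depends on which number of schools applies, and the Protocol gives two.

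**What to change.** In the school-level paragraph under Sample size calculation:

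- Replace the flat 10% by design effect = 1 + (90 − 1) × ICC, and state the ICC and its source. School-level results of the student survey are preferable. The pilot had seven schools and about 235 children (about 34 per school), too few for a precise estimate: at a true ICC near 0.01 the approximate standard error is 0.023.
- Restate the power for the planned number of schools, or the detectable intervention rate from 10%, using small-sample degrees of freedom. For 13 schools per arm at ICC 0.005, 0.01 and 0.02, these are 81%, 70% and 54%, or about 6.1%, 5.6% and 4.8%.
- Keep the statement that power is sufficient only if an ICC of at most about 0.0056 is justified for 13 schools per arm.

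Reconcile the 13 schools per arm in that paragraph with the 9 schools per arm and 1600 children in Data protection and statistical analysis.

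The cost is one recalculation and protocol wording. No extra schools are required; the downside is a less favourable stated power.
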